
CONFIDENTIAL

May not be used, divulged, published or otherwise disclosed without written consent of Arcturus Therapeutics, Inc.

As both COVID-19 and influenza vaccines are recommended to the general population in many countries, the present study is also designed to ensure that neither vaccine interferes with the safety or immunogenicity of the other vaccine when administered concomitantly in adults.

Flucelvax® Quadrivalent (Seqirus Pty Ltd.) is one of the broadly used seasonal influenza vaccines and the only influenza vaccine in use in the United States for which the vaccine viruses are grown in cell culture. This vaccine is licensed for use in individuals 6 months and older.

For individuals 65 years of age and above, there are three influenza vaccines preferentially recommended by the US CDC. They include Fludad® Quadrivalent (Seqirus Pty Ltd.), a standard-dose, inactivated influenza vaccine that contains MF59 (squalene-based oil-in-water adjuvant). An adjuvant is an ingredient added to a vaccine that helps create a stronger immune response to vaccination. Fludad Quadrivalent is licensed for use among people 65 years and older.

The Southern Hemisphere 2024 season vaccine composition for both influenza vaccines will be used in the study. Recent studies ([Domnich et al., 2022](#)) indicate that there are no specific safety concerns raised over administration of mRNA COVID-19 vaccines (such as Pfizer's BNT162b2) in adults alongside standard dose inactivated influenza vaccines, including that with MF59 adjuvant. Concomitant vaccination with both COVID-19 and influenza vaccines should reduce the burden on the healthcare services for vaccine delivery, allowing for timely vaccine administration and protection from COVID-19 and influenza for those in need ([Lazarus et al., 2021](#)).

The study intends to demonstrate that the immune responses against the ARCT-2303 vaccine and the quadrivalent influenza vaccine, when administered concomitantly, are noninferior to immune responses induced when administered separately. These objectives will be demonstrated in individuals 18 to 64 years of age who receive Flucelvax® Quadrivalent. Additional descriptive analysis of co-administration will be performed in participants ≥ 65 years of age who receive adjuvanted influenza vaccine (Fludad® Quadrivalent).

CONFIDENTIAL

May not be used, divulged, published or otherwise disclosed without written consent of Arcturus Therapeutics, Inc.

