2.1.2 Clinical Studies

The current clinical development program incorporates the evaluation of three investigational mRNA SARS-CoV-2 vaccines, developed by Arcturus: ARCT-021, ARCT-154, ARCT-165.

ARCT-021 has been administered to over 700 participants in clinical trials and has been generally well tolerated and immunogenic in studies enrolling healthy younger and older adults.

ARCT-154-01 is a multicenter, Phase 1/2/3 randomized, controlled, observer-blind study designed to evaluate the safety, immunogenicity, and efficacy of ARCT-154 in participants 18 years of age and older in Vietnam. In Phase 3b of the ARCT-154-01 study, a total of 16,120 participants were randomly assigned to receive 2 doses of ARCT-154 or placebo with 8,056 exposed participants in the ARCT-154 group and 8,044 exposed participants in the placebo group.

For participants without evidence of SARS-CoV-2 infection prior to 7 days after Dose 2, overall vaccine efficacy was 56.6% (95% confidence interval [CI]: 48.7% to 63.3%), which met the prespecified success criterion. Vaccine efficacy against severe protocol-confirmed COVID-19 occurring at least 7 days after Dose 2 was 95.3% (95% CI: 80.5% – 98.9%).

In the immunogenicity analysis on Day 57, the study found that 95.9% (95%CI: 93.4 - 97.6) of the ARCT-154 recipients achieved seroconversion after 2 doses as measured by neutralizing antibodies using a microneutralization assay. ARCT-154 vaccine induced broad neutralization of SARS-CoV-2 variants of concern; the seroconversion rates against the most variants at Day 57 (28 days after Dose 2) were above 90% in the ARCT-154 group. GMFR from baseline (Day 1) for most variants at Day 57 was above 10-fold in the ARCT-154 group.

CONFIDENTIAL

ARCT-154-01 has an acceptable safety profile with no major safety concerns in the adult study population:

- Solicited local adverse reactions were reported by 52.4% and 15.3% of Phase 3b participants in ARCT-154 and placebo groups, respectively, within 7 days after the first and second vaccinations. Systemic solicited AEs were reported by 60.6% and 40.9% of participants, respectively.

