#### **Cohort A (participants 18 to 64 years of age; N=1200)**

Individuals will be randomly assigned to one of the three study groups:

[figure not shown]
- Group 1a (ARCT-2303/ Flucelvax Quadrivalent, N=400): participants will receive one dose of ARCT-2303 and one dose of Flucelvax Quadrivalent (opposite arms) on Day 1, and one dose of placebo on Day 29.
- Group 2a (ARCT-2303, N=400): participants will receive one dose of ARCT-2303 and one dose of placebo (opposite arms) on Day 1, and one dose of Flucelvax Quadrivalent on Day 29.
- Group 3a (Flucelvax Quadrivalent, N=400): participants will receive one dose of Flucelvax Quadrivalent and one dose of placebo (opposite arms) on Day 1, and one dose of ARCT-2303 on Day 29.

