**Table 1 Severity Grading for Solicited Local Reactions and Systemic Adverse Events**

	Mild	Moderate	Severe
Pain	No interference with daily activities	Interferes with daily activities	Prevents daily activity
Erythema	25-50 mm	51-100 mm	> 100 mm
Swelling	25-50 mm	51-100 mm	> 100 mm
Fatigue	No interference with daily activities	Interferes with daily activities	Prevents daily activity
Headache	No interference with daily activities	Interferes with daily activities	Prevents daily activity
Myalgia	No interference with daily activities	Interferes with daily activities	Prevents daily activity
Arthralgia	No interference with daily activities	Interferes with daily activities	Prevents daily activity
Nausea	No interference with daily activities	Interferes with daily activities	Prevents daily activity
Dizziness	No interference with daily activities	Interferes with daily activities	Prevents daily activity
Chills	No interference with daily activities	Interferes with daily activities	Prevents daily activity
Fever (°C)	38.0-38.4	38.5-38.9	≥39.0

Note: Based on Food and Drug Administration (FDA) Guidance Document: Toxicity Grading Scale for Healthy Adult and Adolescent Volunteers Enrolled in Preventive Vaccine Clinical Trials.

The following parameters will be summarized by treatment group using descriptive statistics:

- Time to onset of event (first occurrence)
- Duration of event: that is the max duration for those events that have no interruptions during the 7 days (eg if event is on day 1, on day 3, day 4 and day 5 then duration is 3 days. Duration will be calculated considering the stop date from the AEs CRF page for those events that last beyond day 7)

The Solicited AEs will be summarized by treatment group using percentages of participants, overall and by severity (i.e. tables will include any severity, Mild, Moderate and Severe)

- Solicited AEs during 7 days after each vaccination
- Solicited AEs during 7 days after each vaccination overall (any) and by maximum severity (mild, moderate, severe)

Additionally, the following summaries will be provided for Groups 2a and 2b combined (ARCT-2303), Groups 3a and 3b combined (QIV/aQIV):

- Solicited AEs during 7 days post Day 1 vaccination
- Solicited AEs during 7 days post Day 1 vaccination by reaction
- Solicited AEs during 7 days post Day 1 vaccination by grade

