## 7.2 Unsolicited Adverse Events

All unsolicited AEs including SAEs, MAAEs and AESIs will be coded using MedDRA. Medical occurrences that begin before the study vaccination but after obtaining informed consent will be recorded in the medical history/current medical conditions section of the eCRF, not the AE section, all unsolicited AEs collected on the AE CRF page following the first administration will be considered TEAEs and will be included in the summaries.

Summary tables will include the number of participants (%) experiencing an event along with the number of events. Participants will be counted only once for each SOC and PT level (categorical descriptive analysis). All TEAE summaries will be presented by study group, SOC and PT.

The TEAE summaries will include:

- Overview summary of unsolicited AEs (Day 1 – Day 57)
- Summary of unsolicited AEs reported within 30 minutes after each study vaccination (derived by onset date time if event after vaccination date time) by SOC and PT. Please note that for Day 1, when 2 vaccinations are given, the 30 minutes interval is from the second vaccination.
- Summary of unsolicited AE within 28 days after each study vaccination by SOC and PT.
- Summary of related unsolicited AEs within 28 days after each study vaccination by SOC and PT
- Summary of unsolicited AE within 28 days after each study vaccination by SOC, PT and severity.
- Summary of related unsolicited AEs within 28 days after each study vaccination by SOC, PT and severity
- Summary of SAEs by SOC and PT
- Summary of related SAEs by SOC and PT
- Summary of SAEs by SOC, PT and severity
- Summary of related SAEs by SOC, PT and severity
- Summary of MAAEs by SOC and PT
- Summary of related MAAEs by SOC and PT
- Summary of AESIs by SOC and PT
- Summary of related AESIs by SOC and PT
- Summary of AEs leading to discontinuation from study by SOC and PT
- Summary of related AEs leading to discontinuation from study by SOC and PT
- Summary of (S)AEs with fatal outcome by SOC and PT

Additionally, the following summaries up to 28 days post Day 1 vaccination will be provided for Groups 2a and 2b combined (ARCT-2303), Groups 3a and 3b combined (QIV/aQIV):

- Summary of unsolicited AEs by SOC and PT
- Summary of related unsolicited AEs by SOC and PT
- Summary of SAEs by SOC and PT

For final analysis, summary of SAEs, MAAEs, AESI, AE leading to discontinuation and death will be presented cumulatively (Day 1 to EOS).

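### Solicited adverse events are tabulated per vaccination only, so no planned table compares one-visit with two-visit vaccination over both 7-day windows

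*SAP*

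**What the plan says.** SAP 7.1 summarises solicited events by treatment group, with a table described as "Solicited AEs during 7 days after each vaccination overall (any) and by maximum severity (mild, moderate, severe". The word overall there does not mean both visits pooled: the sentence introducing the list explains it as "overall and by severity (i.e. tables will include any severity, Mild, Moderate and Severe". The further summaries in 7.1, for example "Solicited AEs during 7 days post Day 1 vaccination by grade", cover the Day 1 window only. They are for Groups 2a and 2b combined and Groups 3a and 3b combined, and leave out Group 1. Protocol Table 10 (Section 10.3.3) adds no both-window table.

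Under SAP 2.1, Group 1a participants receive "one dose of ARCT-2303 and one dose of Flucelvax Quadrivalent (opposite arms) on Day 1, and one dose of placebo on Day 29". Groups 2a and 3a each receive one active vaccine with placebo on Day 1 and the other active vaccine on Day 29. Cohort B has the same layout with Fluad.

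For other events the SAP does look across visits. Section 7.2 includes an "Overview summary of unsolicited AEs (Day 1 – Day 57") and, at the second final analysis, cumulative summaries of SAEs, MAAEs, AESIs, discontinuations and deaths.

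The secondary safety objective concerns reactogenicity under co-administration or standalone use. The protocol's background rationale adds that the study is designed to ensure that "neither vaccine interferes with the safety or immunogenicity of the other vaccine when administered concomitantly".

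**The concern.** By the end of the Day 29 visit every group has been assigned the same three injections: one ARCT-2303, one influenza vaccine and one placebo. The groups differ in how the two active vaccines are spread over visits. Reactions to both vaccines fall in one window for Group 1 and in two windows for Groups 2 and 3.

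In the Day 1 table, Group 1 is observed after two active vaccines and its comparators after one. More reactions in Group 1 are then expected even if neither vaccine alters the reaction to the other. In the Day 29 table, Group 1 is observed after saline and its comparators after an active vaccine. A reader who wants to know whether more people react when both vaccines are given at one visit than when they are given at two finds no solicited-event table that says so.

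Systemic events are the core of this. Day 1 local reactions are recorded separately for each arm (Protocol 8.12.3), so they can be tied to a vaccine, although 7.1 lists no by-arm table. Fatigue, headache or fever cannot be assigned to an arm.

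**Working it through.** The plan states no figure on this point, so there is none to reproduce. The check compares exposure with the listed tables and then follows the algebra.

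**1. Active vaccines per 7-day window (SAP 2.1)**

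| Group | Day 1 | Day 29 | Both |
|---|---|---|---|
| 1 (a or b) | 2 | 0 | 2 |
| 2 (a or b) | 1 | 1 | 2 |
| 3 (a or b) | 1 | 1 | 2 |

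Assigned exposure is equal only in the last column.

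**2. What the planned tables span**

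| Source | Events | Span |
|---|---|---|
| SAP 7.1, by group | Solicited | Each vaccination separately |
| SAP 7.1, added summaries | Solicited, Groups 2 and 3 pooled over cohorts | Day 1 window only |
| Protocol Table 10 | Solicited | 7 days after vaccination |
| SAP 7.2 | Unsolicited overview | Day 1 to Day 57 |
| SAP 7.2 | SAE, MAAE, AESI, discontinuation, death | Day 1 to end of study |

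No solicited-event row matches the column with equal exposure. Antipyretic use and body temperature are summarised by group with no visit split stated, but neither is named as an across-visit table.

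**3. What the Day 1 difference contains.** Let b be the chance of a background event in a window, a the chance added by ARCT-2303 and q the chance added by the influenza vaccine. Assume that these act independently, with no interaction and no effect of order. The chances of at least one event are:

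- Group 1: Day 1, 1 − (1−b)(1−a)(1−q); Day 29, b.
- Group 2: Day 1, 1 − (1−b)(1−a); Day 29, 1 − (1−b)(1−q).
- Group 3: as Group 2 with the days exchanged.

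The differences follow:

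- Day 1, Group 1 minus Group 2: (1−b)(1−a)q. Group 1 minus Group 3: (1−b)(1−q)a. Both are positive when a, b and q lie strictly between 0 and 1.
- Day 29, Group 1 minus Group 2: −(1−b)q. Group 1 minus Group 3: −(1−b)a. Both are negative.
- Both windows: every group has 1 − (1−b)²(1−a)(1−q), so both differences are 0.

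An excess in Group 1 on Day 1 is therefore what simple addition produces, and interaction would be mixed into the same number. The zero in the last line follows from the assumptions and is not a forecast. In real data the both-window difference would reflect the whole effect of schedule, including any effect of order or timing.

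**4. Whether the planned tables can be combined.** If a group's per-visit proportions are p₁ and p₂₉ in the same participants, the proportion with an event at either visit lies anywhere from max(p₁, p₂₉) to min(1, p₁ + p₂₉). Where it falls depends on how many people reacted twice, which group-level tables do not show. No listings are produced at the first final analysis (SAP 10.1). Someone could link the individual listings after study end, but the initial report would not carry the result.

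**The case against.** The strongest reply is that the SAP delivers the endpoint as the protocol words it: local and systemic events within 7 days of each vaccination. The objective is co-administration or standalone, and the protocol describes Day 29 as a switchover that gives everyone both vaccines and keeps the blind. It does not define Day 29 as the second half of a comparator schedule. The Day 1 comparison is randomised, with two injections in every group, and it answers that objective. All of this stands, and it is why the Day 1 table should be kept. It does not close the gap on the stated aim of non-interference, because the Day 1 difference mixes addition with interaction.

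A reader might infer that the trial cannot say anything about the safety of co-administration. The documents do not support that. Besides the Day 1 contrast and the across-visit tables in SAP 7.2, Protocol 8.12.3 requires solicited events to go on the AE form as well if they lead to a healthcare visit, cause withdrawal, are serious or last beyond 7 days.

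A reader might also try to size the effect from the systemic rates in Protocol 2.1.2 (60.6% ARCT-154, 40.9% placebo) by splitting them equally over two doses. Protocol Table 2 contradicts that split, since it reports generally lower systemic rates after the second dose. Those rates come from a primary series of a different vaccine, and the documents give no influenza-vaccine rate. Nor is that trial's reporting "within 7 days after the first and second vaccinations" a strong precedent: it pooled two doses of one product against placebo and did not compare schedules.

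Table shells are not among the documents and might already hold such a column. The SAP also allows labelled post hoc analyses, so the omission can be repaired later, though without the standing of a prespecified table.

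**Conclusion.** The point holds as a limited, inexpensive improvement. For solicited events, the SAP has per-vaccination tables and none at equal assigned exposure. Its size is structural: 2 and 0 active vaccines per window in Group 1 against 1 and 1 in Groups 2 and 3. No percentage-point figure is offered, because the inputs are not in the documents.

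No hypothesis test, power statement or primary conclusion changes, since safety is descriptive (Protocol 10.1). The conclusion rests on the SAP text as listed, with overall read as any severity, and on the assumption that the unseen table shells add nothing. The algebra shows only that a Day 1 excess is compatible with no interaction. It does not show that interaction is absent.

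**What to change.** In SAP 7.1, add one set of descriptive tables within each cohort and by randomised group (1a, 2a, 3a; 1b, 2b, 3b). Show the number and percentage of participants with each solicited systemic event, any solicited systemic event, and maximum severity over the two 7-day windows combined. Give Group 1 minus Group 2 and Group 1 minus Group 3 differences with 95% CIs, labelled descriptive.

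Use all vaccinated participants, grouped as randomised, for the main version, and state how many have no Day 29 window. A version restricted to participants given both visits' injections may be shown only as a sensitivity analysis. It needs a note that receipt of the Day 29 injection can depend on Day 1 reactions: Protocol 5.3 and 7.1 list adverse events among the reasons for not giving it. Restricting the main table in that way could remove the strongest reactors and lose the protection of randomisation.

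Keep the per-visit tables. Footnote the Day 1 table to say that it compares two active vaccines with one and does not by itself show interaction.

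The cost is SAP wording and one set of tables from eDiary data already planned. There are two small downsides. All-vaccinated participants without a Day 29 window make received exposure not strictly equal. A count of any event also counts someone who is ill at both visits once, which is a further reason to leave the per-visit tables alongside.

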There is no formal hypothesis testing for evaluating the co-administration of ARCT-2303 and Fluad Quadrivalent. The results of the analysis will be presented descriptively.

There is no formal hypothesis testing for the evaluation of the safety objective. Safety will be summarized descriptively within the Safety Analysis Set population.

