5. To assess the immunogenicity of ARCT-2303 vaccine, when administered with or without Fludad Quadrivalent, as measured by virus neutralization assay, in participants $\geq 65$ years of age.	SARS-CoV-2 neutralizing antibody responses against Omicron XBB.1.5 subvariant on Days 1, 29, and 181: 
 
• Co-admin group recipients (Group 1b)
 
• Standalone ARCT-2303 group recipients (Group 2b).
 

6. To assess the immunogenicity of Fluad Quadrivalent when administered with or without ARCT-2303 as measured by HI assay, in participants $\geq 65$ years of age	HI assay titers against influenza vaccine strains on Day 1 and Day 29, in: 
 
• Co-admin group recipients (Group 1b)
 
• Standalone Fluad Quadrivalent group recipients (Group 3b).
 

---	---

a As per FDA guidance: “super” superiority (margin of  $>1.5$ -fold for GMT ratio). US FDA Guidance for Industry. Emergency Use Authorization for Vaccines to Prevent COVID-19. Document issued on March 31, 2022.

The Secondary Safety objective is:

Objective	Endpoints
1. To assess the safety and reactogenicity of the study vaccines when given in co-administration or standalone	
 
• Local and systemic AEs reported within 7 days after each study vaccination
 
• Unsolicited AEs reported within 28 days after each vaccination
 
• SAE, AEs leading to early termination from study, MAAEs, and AESIs during the entire study period (6-month follow-up)
 

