### 3.8 Treatment Groups

Group 1a: ARCT-2303 + QIV  
Group 2a: ARCT-2303 + Placebo  
Group 3a: QIV + Placebo  
Group 1b: ARCT-2303 + aQIV  
Group 2b: ARCT-2303 + Placebo  
Group 3b: aQIV + Placebo  
ARCT-2303 (Gr 2a and 2b)  
QIV/aQIV (Gr 3a and 3b)  
ARCT-154

If any actual treatments received cannot belong to any one of the treatment groups above (e.g. subject receives only one injection), the participant will be summarized under the randomized treatment group.

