## 7 SAFETY

Safety endpoints will be analyzed using the Safety analysis set and will be summarized descriptively as described in section 3.1.

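### Co-administration safety is planned as separate per-group percentages, with no co-administration minus standalone difference and no interval to bound one

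*SAP*

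**What the plan says.** The Protocol Synopsis, under Background and Rationale, states that "the present study is also designed to ensure that neither vaccine interferes with the safety or immunogenicity of the other vaccine"; Protocol 2.1 repeats the aim. The secondary safety objective in SAP 2.2.2 is milder: "To assess the safety and reactogenicity of the study vaccines when given in co-administration or standalone".

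For immunogenicity in Cohort A, co-administration has a 0.67 margin on the GMT ratio, a confidence-limit rule and a power calculation (Protocol 10.1 and 10.2, SAP 13.1).

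For safety, Protocol 10.1 says "There is no formal hypothesis testing for the evaluation of the safety objective", and SAP 7 says "Safety endpoints will be analyzed using the Safety analysis set and will be summarized descriptively as described in section 3.1".

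- Protocol 10.3 plans counts, percentages and a Clopper-Pearson 95% interval for each categorical safety variable.
- SAP 7.1 and 7.2 list percentages and counts by group and do not repeat those intervals.
- SAP 3.1 sets decimal places for intervals and differences but defines no safety contrast.
- Groups 1a and 1b are treatment groups in SAP 3.8, so they appear in every by-group safety table. The additional combined columns are 2a+2b and 3a+3b only. SAP 7.1 has "Additionally, the following summaries will be provided for Groups 2a and 2b combined (ARCT-2303), Groups 3a and 3b combined (QIV/aQIV", SAP 7.2 has the matching sentence for unsolicited events, and the safety subgroups in SAP 3.9 use the same two pools.

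**The concern.** The question about co-administration is comparative: how much more often do reactions occur when both vaccines are given on Day 1 than when one is given with placebo? Allocation is randomised 1:1:1 within each cohort, so an unbiased difference with an interval can be had from data already collected. The plan does not ask for it.

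A reader of the report would have to compare separate columns, each at best with its own interval, and judge whether they look alike. Two columns can look alike while the data remain compatible with a material excess. The gap is widest in participants aged 65 and over, who receive the adjuvanted influenza vaccine and number 160 per arm.

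**Working it through.** **The plan's own figure.** The documents give no power or precision for co-administration safety. The nearest figure is the immunogenicity power in SAP 13.1: 0.97578 for 360 per group, SD 0.60 and margin 0.176 on the log10 scale.

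- Standard error = 0.60 × √(2/360) = 0.0447.
- 0.176/0.0447 − 1.96 = 1.975, giving power 0.9759 (normal); the t-test gives 0.9756. The figure reproduces. It says nothing about safety.

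**Inputs for safety.**
- 400 per arm in Cohort A and 160 in Cohort B (Protocol 4.1), all assumed evaluable.
- Illustrative common rates of 60.6% (systemic) and 52.4% (local) solicited events for ARCT-154 (Protocol 2.1.2). These cover two doses of a primary series in another study, so they are assumptions for a single booster.
- Rates of 5% and 2% are added to show the range; they are also assumptions.

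**Interval when both arms show the same rate p.** The half-width is close to 1.96 × √(2p(1−p)/n).

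- n = 400, p = 0.606: 1.96 × √(2 × 0.606 × 0.394/400) = 1.96 × 0.0346 = 6.8 points.
- n = 160, p = 0.606: 1.96 × √(2 × 0.606 × 0.394/160) = 1.96 × 0.0546 = 10.7 points.

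The Miettinen-Nurminen intervals, computed on the nearest whole counts, agree:

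| Rate in both arms | Cohort A, 400 vs 400 | Cohort B, 160 vs 160 |
|---|---|---|
| 60.6% | ±6.8 points | ±10.7 points |
| 52.4% | ±6.9 | ±10.9 |
| 5% | ±3.1 | ±5.2 |
| 2% | ±2.1 | ±3.7 |

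A 10% loss of participants would widen these by a factor of 1/√0.9 = 1.05.

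**Why per-arm intervals do not do the job.**
- At 400 per arm, 52.5% against 62.25% still gives overlapping Clopper-Pearson intervals, yet the Miettinen-Nurminen interval for the 9.75-point difference is 2.9 to 16.5 points.
- At 160 per arm, 52.5% against 68.1% still overlaps, yet the interval for the difference is 4.9 to 26.0 points.

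Overlap can therefore hide a difference that the data show, and near-equal percentages do not display the excess that the data leave open.

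**The case against.** The strongest reply is that the plan is openly descriptive and nothing in it fails. Much of this stands.

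- **A reader might infer that only bare percentages are planned.** Protocol 10.3 plans an interval for each safety percentage. What is missing is an interval for the difference.
- **A reader might infer that the sponsor plans to claim safety non-interference from similar percentages.** No section says so. The 'ensure' wording is in the rationale, the objective is to assess, and the co-administration success criterion in Protocol 10 is immunogenicity only.
- **A reader might infer that the co-administered arms are left out, or that a combined 1a+1b column is needed.** Both arms are in every by-group table. Combining them would mix an unadjuvanted influenza vaccine in younger adults with an adjuvanted one in older adults, and 400 of the 560 participants would come from Cohort A. That column is not essential.
- **A difference after Day 1 does not isolate interference.** Group 1 has had two active injections; Groups 2 and 3 have had one active and one placebo. Some excess could be simple addition. This stands and governs how the estimate must be labelled.
- **Any reader can work out the interval from the reported counts, and an unblinded DSMB reviews cumulative data.** Both are true. Neither puts the estimate in the report or fixes in advance which contrasts are shown.

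**Conclusion.** The point holds as a gap in estimation. The rationale states a comparative safety aim and the objective covers both ways of giving the vaccines, but no planned output estimates the difference between them.

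With equal observed rates of about 60%, the data would still be compatible with an excess of about 7 points in Cohort A and 11 points in Cohort B. At an assumed 5% rate the figures are about 3 and 5 points. These sizes rest on assumed event rates and full evaluability.

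No figure in the documents is wrong, and no hypothesis or error rate is affected. The documents do not support reading this as a failed or missing safety test: they say that none is intended, and none is needed.

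**What to change.** In SAP 7.1 and 7.2, add descriptive risk differences with two-sided 95% Miettinen-Nurminen intervals for 1a-2a, 1a-3a, 1b-2b and 1b-3b, for:

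- any systemic solicited event within 7 days after Day 1;
- severe systemic solicited events within 7 days after Day 1;
- unsolicited events within 28 days after Day 1.

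Protocol 10.3.2 already names this method for differences in seroconversion rate. Label the intervals as unadjusted for multiplicity, and as the excess of co-administration over either vaccine given with placebo, not as a test of interference. State that any safety conclusion on co-administration will quote the interval. A cohort-stratified pooled difference is optional.

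The cost is some SAP text and a few table columns from data already collected; the downside is twelve more unadjusted intervals (four contrasts × three endpoints). If the first final analysis has already been run, which the documents do not show, report them as post hoc, as SAP 1 provides. If the intervals are not added, align the 'ensure' wording in the Synopsis and Protocol 2.1 with the descriptive objective.
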